**Safety Monitoring Procedures**

- Observation, assessment and recording of reactions by the investigator.
- Evaluations will be done immediately after each treatment and at the follow-up visit. The frequency, severity and causality of all reactions will be recorded.
- Possible Votiva reactions are listed under potential risks.
- Severe and persistent reactions are reportable as adverse events.

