**Study Duration**

Study duration for each subject is approximately four months (including screening, 2 treatment sessions 8 weeks apart and a follow-up visit at 8 weeks post last treatment.

Overall study duration will be approximately 12 months, depending on the subject recruitment rate.

Each subject will undergo 7 study visits including screening, 2 treatment and 1 follow-up visit.

**Visit 1:** Midwest Plastic Surgery-Evaluation

- Screening will be performed to determine subject eligibility as well as to collect all of the required medical information and obtain signed Informed Consent.
- Baseline photographs of the treatment area will be taken
- Pre-procedure questionnaires will be completed at this time
- Time required 1.5 hours

**Visit 2:** Antares Institute-Evaluation

- A complete pelvic floor assessment will be performed including but not limited to the following: measurement of internal and external pelvic floor contraction, measurement of vaginal canal length and diameter, measurement of the introitus, and length of the labia majora and minora. Measurements will be obtained following POP-Q protocol
- This visit will confirm inclusion criteria based on measurements.
- Time required: 1.5hrs

**Visit 3:** Midwest Plastic Surgery – 1st treatment

- Internal and external FormaV treatment
- Photographs of the treatment area will be taken after the procedure.
- Time required: 45 minutes

**Visit 4:** Antares Institute Follow-up visit – 8 weeks following first treatment

- A complete pelvic floor assessment will be performed including but not limited to the following: measurement of internal and external pelvic floor contraction, measurement of vaginal canal length and diameter, measurement of the introitus, and length of the labia majora and minora. Measurements will be obtained following POP-Q protocol.
- Time required: 15 minutes

**Visit 5:** Midwest Plastic Surgery – 2nd treatment

- Photographs of the treatment area will be taken before and after the procedure.
- Questionnaires will be completed.
- Time required: 45 minutes

**Visit 6:** Antares Institute Follow-up visit – 8 weeks following second treatment

- A complete pelvic floor assessment will be performed including but not limited to the following: measurement of internal and external pelvic floor contraction, measurement of vaginal canal

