length and diameter, measurement of the introitus, and length of the labia majora and minora. Measurements will be obtained following POP-Q protocol

- Time required: 15 minutes

**Visit 7:** Midwest Plastic Surgery – Follow-up visit – 8 weeks following second treatment

- Photographs of the treatment area will be taken
- Questionnaires will be completed
- Time required: 45 minutes

- After each treatment and at all visits, adverse events will be recorded.

Duration of each treatment visit is specified.

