#### Exclusion Criteria:

- Internal defibrillator, pacemaker, bladder stimulator or any other implanted electrical device anywhere in the body
- Permanent metal implant in the treatment area
- History of pelvic floor radiation
- Any surgery in the treatment area in the last 3 months
- Current or history of skin cancer, or current condition of any other type of cancer, or pre-malignant moles
- Pregnancy and nursing

- Impaired immune system due to immunosuppressive diseases such as AIDS and HIV, or use of immunosuppressive medications
- Patients with history of diseases stimulated by heat, such as recurrent Herpes Simplex in the treatment area, **may be treated only following a prophylactic regimen.**
- Poorly controlled endocrine disorders, such as diabetes, thyroid dysfunction, polycystic ovary and hormonal virilization
- Any active condition in the treatment area, such as but not limited to open sores, psoriasis, eczema, vitiligo, herpes and rash.
- History of skin disorders, keloids, abnormal wound healing, as well as very dry and fragile skin
- Severe concurrent conditions, such as cardiac disorders, sensory disturbances.
- Use of Isotretinoin (Accutane®) within 6 months prior to treatment.
- Diseases that may be stimulated by light, such as epilepsy, lupus and urticaria.
  
- Any other previous treatments in the vaginal or perineal area, such as CO2 laser or RF performed on the same area.
- Any surgical procedure in the vaginal area within the past 12 months.
- Recent tan from sun, sunbeds or chemicals or planned excessive sun exposure.
- As per the practitioner's discretion, refrain from treating any condition which might make it unsafe for the patient
  
- Participation in this study is not required to receive treatment for pelvic floor relaxation or sexual dysfunction. Patients may receive treatments without participating in the study. Patients may also utilize other methods of treatment including but not limited to Pelvic floor physical therapy, CO2 treatment, or other radiofrequency treatments.

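### No planned contact for about 8 weeks after each treatment: short-lived reactions that start at home rest on recall and are likely to be under-recorded

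*Protocol*

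**What the plan says.** Three statements in the protocol bear on the collection of reactions.

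- **Safety Monitoring Procedures, timing and scope.** The method is "Observation, assessment and recording of reactions by the investigator". The timing and the undertaking are: "Evaluations will be done immediately after each treatment and at the follow-up visit. The frequency, severity and causality of all reactions will be recorded".
- **Safety Monitoring Procedures, reporting.** "Severe and persistent reactions are reportable as adverse events".
- **Study Duration, end of the visit list.** "After each treatment and at all visits, adverse events will be recorded".

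The visit list under Study Duration puts the first treatment at Visit 3 and the second, 8 weeks later, at Visit 5. Visit 4 is 8 weeks after the first treatment. Visits 6 and 7 are both 8 weeks after the second.

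The SAP defines a safety analysis set (everyone treated at least once) and uses observed data without imputation. Its statistical analysis paragraph names no tabulation of reactions.

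**The concern.** The protocol undertakes to record all reactions, with three attributes for each. The schedule lets the investigator see a reaction only on the day of treatment or about 8 weeks afterwards. A reaction that starts some days after the woman goes home and has healed by week 8 is not seen at any planned visit. No visit description tells staff to ask what happened since the last visit.

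The quality of the safety data is at stake. If few or no delayed reactions are reported, the reader cannot tell whether few occurred or few were collected. Because the SAP analyses only what was observed, nothing later in the analysis makes up for what was not collected.

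**Working it through.** **1. Reproduce the stated duration.** Inputs from Study Duration: treatments 8 weeks apart, follow-up 8 weeks after the last treatment. 8 + 8 = 16 weeks = 112 days, and 112 / 30.4375 = 3.7 months. With screening added, this agrees with the stated duration of about four months per subject.

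**2. Place the contacts on that time line** (day 0 = first treatment).

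| Contact | Approximate day |
|---|---|
| Visit 3, first treatment | 0 |
| Visits 4 and 5 (assessment; second treatment) | 56 |
| Visits 6 and 7 (assessment; final follow-up) | 112 |

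This leaves two intervals of about 56 days per woman with no described contact. With at least 20 women (Patient Population and Sample Size), there are at least 20 × 2 = 40 such intervals.

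**3. Set the safety statements side by side.** The rule of recording adverse events at every visit adds no contact inside either interval, because all later visits are at about day 56 or day 112. It does give an occasion to report a healed reaction from memory. Whether such a reaction must then be written down is unclear:

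- If a reaction has to be both severe and persistent to become an adverse event, one that has healed by week 8 may fall outside the recording rule, even if it was severe.
- If either property is enough, a reaction that was neither severe nor persistent still falls outside it.

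On either reading the undertaking to record all reactions is wider than the rule for what becomes an adverse event.

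**4. Illustrate the effect of incomplete capture.** The documents give no capture share, so let *c* be an assumed share of women with a delayed, healed reaction who have it recorded. Take *n* = 20.

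- With no such reaction recorded, the exact one-sided 95% upper limit for the recorded proportion is 1 − 0.05^(1/20) = 13.9%. Dividing by *c* gives the limit for the true proportion.
- If the true proportion is 10% of women (assumed), the chance of recording at least one case is 1 − (1 − 0.10*c*)^20, and the expected number recorded is 20 × 0.10 × *c* = 2*c*.

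| *c* | Upper limit, 0 of 20 recorded | Chance of at least one recorded | Expected recorded, of 2 |
|---|---|---|---|
| 100% | 13.9% | 88% | 2.0 |
| 75% | 18.5% | 79% | 1.5 |
| 50% | 27.8% | 64% | 1.0 |
| 25% | 55.6% | 40% | 0.5 |

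If healed reactions are not recorded at all (*c* = 0), the chance is 0 and a zero count says nothing about the true proportion.

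**The case against.** The case for the plan is substantial, and most of it limits how far the point can be taken.

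- **The undertaking is to record, not to examine while active.** Adverse events are recorded at all visits, so a healed reaction can still be reported at Visits 4 to 7 and given a severity and causality. A reader might infer that the undertaking cannot be met. The documents support only that complete recording is not assured.
- **A 16-week delay for the first treatment.** A reader might infer this from "Each subject will undergo 7 study visits including screening, 2 treatment and 1 follow-up visit". The visit list itself labels Visit 4 a follow-up at 8 weeks, and Objective measurements places follow-up visits 8 weeks after each treatment. The 16-week reading fails.
- **No information before the second treatment.** This does not hold either. Objective measurements schedules an evaluation of genital condition before each treatment, Visit 5 includes photographs before the procedure, and adverse events are recorded at Visits 4 and 5.
- **An expectation of delayed events.** The eligibility text on "Patients with history of diseases stimulated by heat, such as recurrent Herpes Simplex in the treatment area" might suggest that the protocol expects them. It shows that a heat-related recurrence was considered, and it is silent on timing.
- **Visibility at week 8.** With assumed onset on day 3 to 7 and exponential duration with mean 7 to 28 days, exp(−(56 − onset)/mean) gives about 0.1% to 17% still visible on day 56. That is the chance of being seen, under assumed inputs. It ignores recall and is not a capture rate.
- **Incomplete text.** The potential-risks text, the appendices and the consent pages were not supplied. Instructions for reporting from home could be there.
- **Weight.** Safety is not among the listed objectives, and the device is described as FDA-cleared. Immediate reactions are evaluated directly, and persistent ones remain observable.

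What remains is the 8-week interval itself, the lack of any described method for eliciting reactions within it, and the mismatch between the reaction and adverse-event statements.

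**Conclusion.** The point holds as a limited, practical weakness. The supplied text describes no planned contact for about 56 days after each treatment and no method for eliciting reactions in that time. Reactions that start at home and resolve before week 8 depend on recall at Visits 4 to 7. Their date, severity and causality will be less reliable, and their frequency is likely to be under-recorded.

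The interval length and the count of at least 40 intervals come from the protocol. The size of the under-recording is not known: the capture shares and the 10% proportion in the table are assumptions, and women are treated as independent. The conclusion also assumes that no collection method sits in the text not supplied. The statements on reactions and on adverse events need to be reconciled whether or not it does.

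**What to change.** 1. At Visits 3 and 5, give each woman a one-page dated symptom diary for the following 8 weeks: symptom, start, stop, severity, any care sought. Review it with her at Visits 4/5 and 6/7 and enter it in the reaction record.
2. Amend Safety Monitoring Procedures to name the diary and Visits 4 to 7 as sources, in line with the recording rule at the end of Study Duration. State what is collected for a reaction that has already healed, and reconcile this with the sentence on which reactions become adverse events.
3. In the SAP, report immediate reactions and interval (delayed) reactions separately for each treatment session.

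The cost is one form, a short amendment and a small burden on participants, with no added visit, staff or procedure. The reported reaction rate will probably rise. Diary severity is self-rated and reaches staff no earlier than the existing visits, so the change improves completeness and dating but does not supply direct examination.

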**Patient Population and Sample Size**

At least 20 female subjects ages 35-75 selected based on evaluation of symptoms including the following: urinary incontinence, pelvic floor laxity.

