Cover Letter:

All enclosed below documents are part of the clinical trial NCT03536819

Study Name: Radio-frequency rejuvenation for pelvic floor and vagina

Protocol No.: DO607404A

Document date: September 20, 2017

SPONSOR: InMode Ltd.

[name]

[name]

[name]

[name]

[contact]

[contact]

I. Data analysis.

A. Analysis Sets

1. Safety Analysis Set

a) The safety analysis set will include all subjects using Votiva procedures at least a single time.

2. Performance Analysis Set

a) Performance analysis set will consist of all subjects providing at least one post treatment performance measurement.

3. Treatment of Missing Values

a) Only observed data will be used; i.e. missing data will not be imputed.

B. Statistical Analysis

1. Means, and standard deviations for each characteristic will be calculated. Paired sample t-test will be computed to assess changes in before treatment and follow-up scores. Statistical significance will be calculated and two-tail significance level of 0.05 will be used. All analyses will be conducted using IBM SPSS 21.0.

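### Does the lack of a planned safety summary mean that milder reactions would drop out of the safety result?

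*Protocol*

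**What the plan says.** The Protocol's Safety Monitoring Procedures have the investigator observe, assess and record reactions right after each treatment and at follow-up. They add: "The frequency, severity and causality of all reactions will be recorded". The section then refers to a list elsewhere ("Possible Votiva reactions are listed under potential risks") and ends with "Severe and persistent reactions are reportable as adverse events". The visit schedule under Study Duration closes with a separate instruction: "After each treatment and at all visits, adverse events will be recorded".

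The SAP, section I.A.1, fixes the population: "The safety analysis set will include all subjects using Votiva procedures at least a single time". Section I.B then gives the analyses: "Means, and standard deviations for each characteristic will be calculated" and "Paired sample t-test will be computed to assess changes in before treatment and follow-up scores", with a two-sided 0.05 level and the software. It assigns no analysis to the safety set by name.

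**The concern.** Neither analysis in SAP I.B yields a safety result. A mean and standard deviation do not give the number of women who had a reaction, or how severe it was or what caused it. A paired t-test has nothing to work on, because a treatment reaction has no pre-treatment score. The safety set is therefore defined and then not visibly used.

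In the supplied text, the only sentence that links reactions to adverse events is the one about severity and persistence. If an author took it as the definition of an adverse event and reported only adverse events, milder and transient reactions would be on the case report forms but not in the result. Two teams could then report different safety results from identical data, and the less favourable picture would be the one left out.

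**Working it through.** The plan states no safety rate, threshold or power figure, so there is nothing of its own to reproduce. The check is mainly a comparison of the texts.

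**1. What is recorded.** Safety Monitoring Procedures cover all reactions, with frequency, severity and causality. A mild, transient reaction is therefore captured.

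**2. What the narrower sentence excludes.** A mild, transient reaction is neither severe nor persistent, so it falls outside whether both conditions are needed or either one is enough. If both are needed, severe but brief reactions and mild but lasting ones fall outside too.

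**3. What the narrower sentence governs.** It says which reactions are *reportable*. That can mean passed on to a sponsor or authority, or it can mean counted in the results. The documents do not say which. On the first meaning, the sentence puts no limit on what is tabulated.

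**4. Whether the Protocol sections conflict.** They do not. One tier records every reaction; a second reports some of them as adverse events. The Study Duration instruction sets when adverse events are recorded and does not narrow the first tier.

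**5. What an analyst would have in hand.** The numerator is women with a recorded reaction, classified by severity and causality. The denominator is the safety set in SAP I.A.1. Only the instruction to divide one by the other is unwritten.

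**6. Size, under assumptions.** Take n = 20 from Patient Population and Sample Size ("At least 20 female subjects ages 35-75 selected based on evaluation of symptoms"). Assume that no reaction meets the narrower wording and that x women have a milder one. The exact (Clopper-Pearson) 95% limits are the 2.5th percentile of Beta(x, n − x + 1) and the 97.5th percentile of Beta(x + 1, n − x). For x = 0 the lower limit is 0 and the upper limit is 1 − 0.025^(1/20) = 16.8%.

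| Women with a reaction (assumed) | Percent | Exact 95% CI |
|---|---|---|
| 0 of 20 (narrower count) | 0% | 0 to 16.8% |
| 1 of 20 | 5% | 0.1 to 24.9% |
| 5 of 20 | 25% | 8.7 to 49.1% |
| 10 of 20 | 50% | 27.2 to 72.8% |
| 15 of 20 | 75% | 50.9 to 91.3% |

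The counts are invented for illustration. They show that a different numerator gives a different percentage. They do not show that the narrower numerator would be used.

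**The case for a change.** The best case for a change is that a SAP exists to settle outputs before the data are seen, and this one does so for the scores but not for safety. Stretching the phrase about each characteristic to cover reactions does not help, since means and standard deviations are the wrong summary. Even if the severity-and-persistence sentence concerns only notification, the SAP still names no safety table. One sentence and one table would close the gap, using data already required, with no new visit or procedure.

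Most of this stands as description. SAP I.B is silent on safety, and a fuller SAP would not be. What does not stand is the step from silence to a biased result. That step needs three things the documents do not supply: that the sentence defines what counts in the results, that the report will be confined to it, and that the reactions recorded in full will not be shown. The supplied text also lacks the potential-risks list to which the Protocol refers. A fuller definition there cannot be checked, and its absence counts neither for nor against the plan.

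**Conclusion.** No change is needed. This is a missing detail of output that analysts fill sensibly: the data are required, the denominator is defined, and in a study of about 20 women the natural summary is a count or listing of all recorded reactions by severity and causality. No data are lost, the Protocol sections do not contradict each other, and no stated rule or number comes out wrong. The Study Objectives concern muscle contraction, symptoms, quality of life and satisfaction. The supplied documents set no safety hypothesis or threshold, so no planned test or efficacy conclusion depends on the point.

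The size of any under-reporting cannot be derived from the documents; the 5% to 75% range rests wholly on assumed counts. The conclusion assumes that reactions are recorded as the Protocol requires and that the safety result draws on those records. If a report gave only events meeting the narrower wording, without saying so, that would be a fault in the report. The plan does not call for it.

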**Patient Population and Sample Size**

At least 20 female subjects ages 35-75 selected based on evaluation of symptoms including the following: urinary incontinence, pelvic floor laxity.

**Study Duration**

Study duration for each subject is approximately four months (including screening, 2 treatment sessions 8 weeks apart and a follow-up visit at 8 weeks post last treatment.

Overall study duration will be approximately 12 months, depending on the subject recruitment rate.

Each subject will undergo 7 study visits including screening, 2 treatment and 1 follow-up visit.

**Visit 1:** Midwest Plastic Surgery-Evaluation

- Screening will be performed to determine subject eligibility as well as to collect all of the required medical information and obtain signed Informed Consent.
- Baseline photographs of the treatment area will be taken
- Pre-procedure questionnaires will be completed at this time
- Time required 1.5 hours

**Visit 2:** Antares Institute-Evaluation

- A complete pelvic floor assessment will be performed including but not limited to the following: measurement of internal and external pelvic floor contraction, measurement of vaginal canal length and diameter, measurement of the introitus, and length of the labia majora and minora. Measurements will be obtained following POP-Q protocol
- This visit will confirm inclusion criteria based on measurements.
- Time required: 1.5hrs

**Visit 3:** Midwest Plastic Surgery – 1st treatment

- Internal and external FormaV treatment
- Photographs of the treatment area will be taken after the procedure.
- Time required: 45 minutes

**Visit 4:** Antares Institute Follow-up visit – 8 weeks following first treatment

- A complete pelvic floor assessment will be performed including but not limited to the following: measurement of internal and external pelvic floor contraction, measurement of vaginal canal length and diameter, measurement of the introitus, and length of the labia majora and minora. Measurements will be obtained following POP-Q protocol.
- Time required: 15 minutes

**Visit 5:** Midwest Plastic Surgery – 2nd treatment

- Photographs of the treatment area will be taken before and after the procedure.
- Questionnaires will be completed.
- Time required: 45 minutes

**Visit 6:** Antares Institute Follow-up visit – 8 weeks following second treatment

- A complete pelvic floor assessment will be performed including but not limited to the following: measurement of internal and external pelvic floor contraction, measurement of vaginal canal

length and diameter, measurement of the introitus, and length of the labia majora and minora. Measurements will be obtained following POP-Q protocol

- Time required: 15 minutes

**Visit 7:** Midwest Plastic Surgery – Follow-up visit – 8 weeks following second treatment

- Photographs of the treatment area will be taken
- Questionnaires will be completed
- Time required: 45 minutes

- After each treatment and at all visits, adverse events will be recorded.

Duration of each treatment visit is specified.

